### **10.6 SAE Reporting process**

On becoming aware that a participant has experienced an SAE which requires reporting on an SAE form, the PI or delegate should report the SAE to their own Trust in accordance with local practice and to the TONIC Trial Office.

To report an SAE to the TONIC Trial Office, the PI or delegate must complete, date and sign the SAE Form via the TONIC EDC Trial system using the information below within the timeline specified in sections 10.5.3. Any other relevant, appropriately anonymised, data should be submitted to the TONIC Trial Office using the TONIC Trial Mailbox ([[contact]](mailto:[contact])).

**To report an SAE, the PI or delegate should:**

**Complete the SAE form via the TONIC trial EDC system**

**Please also Email [[contact]](mailto:[contact]) to make the TONIC Trial Office aware that an SAE has been submitted, along with any other relevant anonymised documentation.**

Where an SAE Form has been completed by someone other than the PI (or medically qualified delegate) initially, the original SAE form must be countersigned by the PI to confirm agreement with the causality and severity assessments.

On submission of an SAE form, a unique reference number will be assigned. The site and the TONIC Trial office should ensure that the SAE reference number is quoted on all

---

correspondence. The site should e-mail the trial mailbox to inform the TONIC Trial office that they have submitted an SAE.

If the site has not received confirmation of receipt of the SAE or if the SAE has not been assigned a unique SAE reference number within 1 working day of reporting, the site should contact the TONIC Trial Office.

Copies of the completed SAE form should be printed on resolution of the SAE and filed in the ISF.

### **10.6.1 Assessment of causality of an SAE**

When completing the SAE form, the PI (or, throughout this section, a medically qualified delegate) will be asked to define the nature of the seriousness and causality (relatedness; see Table 10: Categories of causality) of the event.

In defining the causality the PI must consider if any concomitant events or medications may have contributed to the event and, where this is so, these events or medications should be reported on the SAE form. It is not necessary to report concomitant events or medications which did not contribute to the event.

As per Table 10, all events considered to be 'possibly', 'probably', or 'definitely' related to the intervention (i.e. early PN) or operation, will be reported by the trial office as 'related'; all events considered at site to be 'unlikely' or 'unrelated' to the intervention will be reported by the trials office as 'unrelated'. The same categorisation should be used when describing AEs and protocol-exempt SAEs in the source data.

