## **Secondary Objectives**

Secondary objectives are to:

- Assess the impact of early PN on post-operative complications up to 90 days post-operation
- Assess the impact of early PN on activities of daily living up to 90 days post-operation
- Assess the impact of early PN on muscle function with sit to stand test at hospital discharge
- Assess the impact of early PN on patient reported outcomes (gastrointestinal recovery (PRO-diGI), quality of recovery (QoR-15)) up to 90 days post-operation
- Assess the rate of SAE related to early PN up to 89 days post-operation
- Assess the impact of early PN on unplanned readmissions following discharge up to 90 days post-operation
- Assess the impact of early PN on hospital length of stay during index admission
- Assess the impact of early PN on discharge destination following index admission
- Assess the impact of early PN on participant satisfaction with treatment
- Report PN use in both arms, including duration and calories administered
- Report use of any nutritional intervention in either trial arm
- Report pathway metrics related to randomisation, line insertion, operation, and time to starting PN.

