### 3.4 Assessment of risk

Participants in both arms will be undergoing emergency laparotomy/laparoscopy as part of their standard medical care. The trial intervention is PN with the main risks relating to changes in blood electrolytes, high blood sugar, liver function changes (cholestasis), and potential infection of the peripherally inserted central catheter (PICC) line. These risks are generally manageable and monitored closely by healthcare professionals to prevent any lasting impact. The risks of PN will be mitigated through regular monitoring and adjustments of blood electrolytes and blood sugar levels, careful management of liver function and strict infection control measures for the PICC line.

All clinical trials can be considered to involve an element of risk and in accordance with the Birmingham Clinical Trials Unit (BCTU) standard operating procedures this trial has been risk assessed to clarify any risks relating uniquely to this trial beyond that associated with usual care. A Risk Assessment has been conducted and concluded that this trial corresponds to the following categorisation: No higher than the risk of standard medical care.

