## 10. ADVERSE EVENT REPORTING

### 10.1 Definitions

Table 5: Definitions for Adverse Events

|   |          |   |
|---|----------|---|
| Severity Definitions                         | Mild     | Awareness of signs or symptoms that do not interfere with the participant's usual activity or are transient and resolved without treatment and with no sequelae.  |
|   | Moderate | A sign or symptom, which interferes with the participant's usual activity.  |
|   | Severe   | Incapacity with inability to do work or perform usual activities (including life threatening events and fatality).  |
| Adverse Event                                | AE       | Any untoward medical occurrence in a participant participating in the trial which does not necessarily have a causal relationship with the intervention received.   |
| Related Event                                | RE       | An event which resulted from the administration of any of the research procedures.  |
| Serious Adverse Event                        | SAE      | An untoward occurrence that:
Results in death
Is life-threatening*
Requires hospitalisation or prolongation of existing hospitalisation
Results in persistent or significant disability or incapacity
Consists of a congenital anomaly/ birth defect
Or is otherwise considered medically significant by the Investigator** |
| Unexpected Event                             | UE       | The type of event that is not listed in the protocol as an expected occurrence.   |
| Related and Unexpected Serious Adverse Event | N/A      | A SAE that meets both the definition of a Related and Unexpected Event.   |

\* The term life-threatening is defined as diseases or conditions where the likelihood of death is high unless the course of the disease is interrupted.

\*\* Medical events that may not be immediately life-threatening or result in death or hospitalisation but may jeopardise the participant or may require intervention to prevent one of the other outcomes listed in the definitions above.

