## **10.3 Adverse event reporting period**

The reporting period for AEs and Serious Adverse Events (SAEs) in TONIC will be:

- For PN related SAEs: from the day of PN until the end of the trial (90 days post-operation).
- For surgery related SAEs: from the day of surgery until the end of the trial (90 days post-operation).

The overall defined reporting period will end 90 days post-operation. After the participant has reached 90 days post-operation, sites will not be actively following up participants for SAEs.

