**Table 10: Categories of causality**

| Category   | Definition  | Causality |
|------------|---|-----------|
| Definitely | There is clear evidence to suggest a causal relationship, and other possible contributing factors can be ruled out.   | Related   |
| Probably   | There is evidence to suggest a causal relationship, and the influence of other factors is unlikely.   |           |
| Possibly   | There is some evidence to suggest a causal relationship. However, the influence of other factors may have contributed to the event (e.g., the participant's clinical condition, other concomitant events or medication) |           |

|             |   |           |
|-------------|---|-----------|
| Unlikely    | There is little evidence to suggest there is a causal relationship. There is another reasonable explanation for the event (e.g., the participant's clinical condition, other concomitant events or medication). | Unrelated |
| Not related | There is no evidence of any causal relationship.  |           |

On receipt of an SAE Form, the Trial Office will notify the Chief Investigator (CI) or delegate of the SAE including details of the unique reference number, who will independently\* review the causality of the SAE. An SAE judged by the PI or CI or delegate to have a reasonable causal relationship ("Related" as per Table 10: Categories of causality) with the intervention will be regarded as a related SAE. The severity and causality assessment given by the PI will not be downgraded by the CI or delegate. If the CI or delegate disagrees with the PI's causality assessment, the opinion of both parties will be documented, and where the event requires further reporting, the opinion will be provided with the report.

\*Where the CI is also the reporting PI, an independent clinical causality review will be performed.

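### The causality rules in section 10.6.1 overlap: an SAE attributed to the operation but not to PN is both 'related' and 'unrelated', and the reported flag does not isolate PN-related SAEs

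*Protocol*

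**What the plan says.** Section 10.6.1 contains one sentence with two rules. Events at least possibly "related to the intervention (i.e. early PN) or operation, will be reported by the trial office as 'related". In the second half, "all events considered at site to be 'unlikely' or 'unrelated' to the intervention will be reported by the trials office as 'unrelated". The first rule names the operation and the second does not.

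Three other places bear on the same word:

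- The paragraph after Table 10 says that an SAE which the PI, or the CI or delegate, judges to have a reasonable causal relationship "with the intervention will be regarded as a related SAE". The operation is not mentioned.
- Table 5 (section 10.1) defines a Related Event as "An event which resulted from the administration of any of the research procedures". Section 3.4 states: "Participants in both arms will be undergoing emergency laparotomy/laparoscopy as part of their standard medical care".
- Section 10.3 sets reporting periods for two separate classes, PN-related and surgery-related SAEs, the first being "For PN related SAEs: from the day of PN until the end of the trial (90 days post-operation".

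One of the secondary objectives in section 2.2.1 is: "Assess the rate of SAE related to early PN up to 89 days post-operation". (The 89 days there against 90 days in section 10.3 is a separate matter.)

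**The concern.** Relatedness is a working rule that sites and the trial office apply event by event while the trial runs, so a later analysis plan cannot settle it. It has two uses.

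First, the secondary objective asks for SAEs related to early PN. A flag that also turns positive for surgical causes does not measure that, and it can be positive in control participants who never received PN.

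Second, it steers reporting. Under section 10.6.2 related SAEs are assessed for expectedness. Under section 10.5.3 SAEs outside Table 9 need expedited reporting if they are related and unexpected. Under section 10.7 related and unexpected SAEs go to the REC within 15 days. If 'related' has more than one meaning, two sites can handle the same event differently and both be following the protocol.

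**Working it through.** There is no stated figure to reproduce. The check is whether the rules give each event one label.

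**Inputs.** Table 10 has five categories: definitely, probably, possibly (grouped as related), unlikely, not related (grouped as unrelated). Judge each event once against PN and once against the operation: 5 × 5 = 25 combinations.

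**Applying each rule.**

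- Section 10.6.1, 'related' (PN or operation at least possibly): 25 − 2 × 2 = 21 combinations.
- Section 10.6.1, 'unrelated' (PN unlikely or not related, operation ignored): 2 × 5 = 10.
- Both at once (PN unlikely or not related, operation at least possibly): 2 × 3 = 6. Check: 21 + 10 − 6 = 25.
- Text after Table 10, 'related' (intervention only): 3 × 5 = 15. The 6 overlapping combinations are exactly the difference, 21 − 15.
- Table 5: the operation is standard care by section 3.4, so on a plain reading the same 6 are not related there either.

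These are counts of logical combinations and say nothing about how often each occurs.

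**Charitable reading.** Suppose 'the intervention' in the second rule is shorthand for 'PN or the operation'. The overlap then disappears (21 related, 25 − 21 = 4 unrelated). The flag still pools the two causes, and it still disagrees with the text after Table 10 (21 against 15).

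**Events that reach the rule.**

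- *Death.* Table 9 puts every death on the SAE form, where causality must be given. At the 9.6% 90-day mortality quoted in section 1.1, 0.096 × 449 is about 43 deaths per arm and 0.096 × 898 about 86 in all. This assumes that the audit rate applies to the trial. The share falling in the 6 overlapping combinations is not given, so the affected number lies anywhere between 0 and about 86. Table 9 requires expedited reporting of a death whatever the flag says and lists death as expected, so for deaths it is mainly the related label that is unsettled.
- *A surgical complication not listed in Table 7.* Section 1.2.3 foresees enterocutaneous fistula, which Table 7 does not list. Table 8 lists surgical complications generally, but only for participants allocated to PN. Take a control participant who received no PN and has a fistula recorded as such and attributed to the operation. It is related under the first rule. It could also be unexpected, because the sentence below Table 11 treats an event not defined in the protocol as expected in that way. Under the text after Table 10 it is unrelated and does not go to the REC.

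**The case against.** The strongest reply is that little rides on this sentence. Table 7 sends 16 common surgical complications to trial-specific CRFs, and Table 6 exempts disease-related SAEs. Table 8 collects the recognised metabolic and line complications in the PN arm, and section 9.1 schedules nutrition-related complications to day 90. Section 10.3 keeps PN-related and surgery-related SAEs apart, and the SAE form, which is not shown, may already do so. The safety summary in section 14.2.2 counts patients with SAEs by arm without using relatedness. A PN line may be placed at operation (section 7.2), so broad capture can be defended as caution.

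Much of this stands, and it rules out three stronger inferences that a reader might draw:

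- *That the PN-related SAE rate cannot be obtained.* The text after Table 10, section 10.3 and Table 8 all offer routes to it, and the form is unseen.
- *That the flag would overstate the PN-related rate several-fold.* That needs surgical SAE rates on the SAE form, which the documents do not give and which Tables 6 and 7 would keep well below overall morbidity. An anastomotic leak, for instance, is a Table 7 event and goes on another CRF.
- *That the REC would be flooded.* Tables 7 and 8 define most surgical events as expected, and Table 11 also counts as expected whatever is consistent with known information on trial-related procedures.

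Section 10.5 also contains a broader sentence, sending every SAE outside the exempt and non-expedited groups to section 10.5.3. On that reading expedited reporting of an unlisted SAE would not depend on the flag; expectedness review and REC reporting still would.

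The reply does not remove the contradiction. Table 8 covers listed events in one arm and does not replace a causality judgement. Section 10.6.1 also asks for the same categorisation of AEs and exempt SAEs in source data, so the ambiguity carries over there.

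**Conclusion.** The point holds as a contradiction in a stated rule. Six of 25 causality combinations are both related and unrelated under section 10.6.1, and the same six are related there but not under the text after Table 10 or, given section 3.4, under Table 5. As worded, the reported flag does not isolate PN-related SAEs. For an operation-attributed SAE outside Tables 6 to 8, expectedness review and REC reporting depend on the sentence read, as does expedited reporting on the wording of section 10.5.3.

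The size in participants is unknown, because the documents give no rates by cause. The effect is confined to safety reporting and one secondary objective; the primary CCI comparison is untouched. The by-arm SAE counts do not use the flag directly, although under section 10.5.3 it can help decide whether an unlisted SAE is sent in. The conclusion rests on the protocol wording alone. If the SAE form already records the two causes separately, only the text needs correcting.

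**What to change.** - Reconcile Table 5, the two rules in section 10.6.1 and the paragraph after Table 10, so that 'related' and 'unrelated' are complements and mean the same throughout.
- On the SAE form, record two separate Table 10 judgements: causality to PN, including the line placed to deliver it, and causality to the index operation. Both may be positive for one event, which deals with lines placed at operation.
- Use the PN field for the secondary objective on SAEs related to early PN.
- State which field or fields define 'related' for sections 10.5.3, 10.6.2 and 10.7, consistent with the two classes in section 10.3. Restricting 'related' to PN for every purpose would drop the surgery-related class that section 10.3 includes, so this needs an explicit decision.

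The cost is a wording amendment, one extra form field and slightly more work for the PI per SAE. It is best done before SAEs accumulate, since a separate PN judgement is hard to reconstruct reliably afterwards.

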**Table 10: Categories of causality**

| Category   | Definition  | Causality |
|------------|---|-----------|
| Definitely | There is clear evidence to suggest a causal relationship, and other possible contributing factors can be ruled out.   | Related   |
| Probably   | There is evidence to suggest a causal relationship, and the influence of other factors is unlikely.   |           |
| Possibly   | There is some evidence to suggest a causal relationship. However, the influence of other factors may have contributed to the event (e.g., the participant's clinical condition, other concomitant events or medication) |           |

|             |   |           |
|-------------|---|-----------|
| Unlikely    | There is little evidence to suggest there is a causal relationship. There is another reasonable explanation for the event (e.g., the participant's clinical condition, other concomitant events or medication). | Unrelated |
| Not related | There is no evidence of any causal relationship.  |           |

On receipt of an SAE Form, the Trial Office will notify the Chief Investigator (CI) or delegate of the SAE including details of the unique reference number, who will independently\* review the causality of the SAE. An SAE judged by the PI or CI or delegate to have a reasonable causal relationship ("Related" as per Table 10: Categories of causality) with the intervention will be regarded as a related SAE. The severity and causality assessment given by the PI will not be downgraded by the CI or delegate. If the CI or delegate disagrees with the PI's causality assessment, the opinion of both parties will be documented, and where the event requires further reporting, the opinion will be provided with the report.

\*Where the CI is also the reporting PI, an independent clinical causality review will be performed.

### 10.6.2 Assessment of expectedness of an SAE by the CI

The CI or delegate(s) will also assess all related SAEs for expectedness with reference to the criteria in Table 11: Categories of expectedness.

**Table 11: Categories of expectedness**

| Category   | Definition  |
|------------|---|
| Expected   | An adverse event that is consistent with known information about the trial related procedures or that is clearly defined in the relevant safety information |
| Unexpected | An adverse event that is not consistent with known information about the trial related procedures.   |

If the event is unexpected (i.e., it is not defined in the protocol as an expected event) it will be classified as a related and unexpected SAE.

The CI will undertake review of all SAEs and may request further information from the clinical team at site for any given event(s) to assist in this.

### **10.6.3 Provision of SAE follow-up information**

Following reporting of an SAE for a participant, the participant should be followed up until resolution or stabilisation of the event. Follow-up information should be provided using the SAE reference number provided by the Trial Office. Once the SAE has been resolved, all critical follow-up information has been received, where significant new information is reported, the PI (or medically qualified delegate) should also consider review and update of relatedness and causality as applicable.

## **10.7 Reporting SAEs to third parties**

The independent Data Monitoring Committee (DMC) may review any SAEs at their meetings.

The TONIC Trial Office will submit a progress report to the REC and Sponsor annually starting 12 months after the date of the favourable opinion was given. An electronic copy should be emailed to the REC within 30 days of the end of the reporting period.

The Trial Office will report all events categorised as Unexpected and Related SAEs to the REC and UoB RGT within 15 days of being notified.

Details of all Unexpected and Related SAEs, and any other safety issue which arises during the course of the trial will be reported to the PIs. A copy of any such correspondence should be filed in the ISF and Trial Master File (TMF).

## **10.8 Urgent Safety Measures**

If any urgent safety measures are taken, the Trial Office shall immediately, and in any event no later than 3 days from the date the measures are taken, give written notice to the REC of the measures taken and the reason why they have been taken.

## **10.9 Follow-up of pregnancy outcomes for potential SAEs**

Any participants that become pregnant from the date that PN (intervention) is started until 30 days after the last administration will be followed up to outcome of the pregnancy. The outcome of these pregnancies will be recorded via the pregnancy notification form and in the event of congenital anomalies or birth defects these should be reported as an SAE.

## 11. DATA HANDLING AND RECORD KEEPING

### 11.1 Source data

Source data is defined as all information in original records and certified copies of original records of clinical findings, observations, or other activities in a clinical trial necessary for the reconstruction and evaluation of the trial. In order to allow for the accurate reconstruction of the trial and clinical management of participants, source data will be accessible and maintained.

Typically, the data provided on all eCRFs should routinely be recorded in the participant's medical notes, when this is not being conducted then data collected for the purpose of TONIC can be recorded on paper worksheets. Data should then be transcribed into the Trial EDC system and the data on paper worksheet will be considered the source data and should subsequently be filed in the ISF.

The data variables listed below (Table 12) will be collected as described in the source column. All other data will be collected into the patient record and transcribed into the eCRF. Where connectivity to the internet is an issue Worksheets will be provided to back up the eCRF within the EDC system.

